#### **4.5.2.2 Missing Data at Baseline for Efficacy and Safety Endpoints**

For efficacy endpoints (including CRP and ESR), a missing value at baseline will not be imputed with the screening results for change from baseline or percent change from baseline calculations; the endpoint will be missing for all visits.

For safety endpoints, a missing value at baseline will be imputed using the prior result that is closest in proximity to baseline in order to calculate change from baseline or percent change from baseline.

#### **4.5.2.3 Multiple Imputation: Predictive Mean Matching**

For further sensitivity analyses for DAS28(CRP), multiple imputation may be conducted (see section [4.9.2](#)). If needed, this will be conducted as an ad-hoc analysis by GSK.

The multiple imputation procedure will assume that the observed visit data are from a multivariate normal distribution and that data are missing at random. Depending on the missing data pattern, either the predicted mean matching method (monotone missing pattern) or the MCMC method (either monotone or non-monotone missing pattern) for imputation will be used.

The sensitivity analysis will follow steps 1 to 3:

1. Using PROC MI, missing data will be filled in  $m$  times to generate  $m$  complete datasets using the observed data. If the MCMC method is used, specify IMPUTE=FULL to impute all missing values.

2. Change from baseline will be calculated in each of the  $m$  complete datasets and then analyzed using the appropriate dose response model identified at the second interim analysis.
3. Using PROC MIANALYZE, the  $m$  sets of estimated parameters from the dose response model will be combined to form the mean and standard deviation of each parameter for use in inference regarding the dose response relationship at Weeks 24 or 52 visits.

#### **4.5.3 Multiple Assessments and Early Withdrawal Visits**

If a variable has been assessed multiple times at the same visit, only the last assessment will be used except for Electrocardiograms (ECGs) or laboratory measurements. Triplicate ECG measures will be averaged for each subject and visit prior to generating summary tables.

For laboratory values the value with the worst CTCAE grade will be considered. If there is more than one value of this grade, the later value will be considered.

Only scheduled visits will be included in summaries. Listings will include scheduled and unscheduled visits.

Early Withdrawal (EW) visits will be assigned to the respective visit according to the Time and Events table in Section 7.1 of the protocol using the day of the EW visit relative to Day 1. For the first 4 weeks an EW visit more than  $\pm 3$  days in comparison to the target visit will be assigned to the closest target visit. Starting with Week 4, an EW visit more than 7 days after a target visit day will be assigned to the next visit.

If a scheduled visit and an EW visit occur within the same visit window and are both available, the later visit will be used for analyses. The earlier visit will appear in listing only. For efficacy analyses, if an EW visit is assigned to a non-standard efficacy visit, i.e., a visit at which efficacy assessments are not scheduled per the Time and Events Table, then these EW data will be ignored in the statistical analysis.

#### **4.5.4 Oral Corticosteroid Conversion**

To assess corticosteroid use and determine average daily corticosteroid dose, all corticosteroid dosages will be converted to a prednisone equivalent in milligrams by multiplying the dose of the steroid (using the coded term from GSKDrug) by the conversion factor to get prednisone equivalent units. Summaries refer to average daily prednisone dose instead of average daily corticosteroid dose. See [Table 3](#) for conversion factors.

**Table 3 Corticosteroid Conversion Factors**

Conversion	Steroid
8.333	BETAMETHASONE
8.333	BETROSPAM
0.2	CORTISONE
8.333	CRONOLEVEL
0.83333	DEFLAZACORT
6.667	DEXAMETHASONE
0.25	HYDROCORTISONE
1.25	MEPREDNISONE
1.25	METHYLPREDNISOLONE
2.5	PARAMETHASONE
1	PREDNISOLONE
1	PREDNISONE
1.25	TRIAMCINOLONE

For each scheduled visit, the average daily prednisone dose will be calculated by summing all oral corticosteroid doses (converted to prednisone) since the previous visit up to and including the current visit and then dividing by the number of days in this period (Date of current visit – Date of previous scheduled visit).

#### **4.6 Demographic and Other Baseline Characteristics**

The following Baseline characteristics will be summarised based on the ITT population by randomised treatment group.

##### Demographic Characteristics

Continuous variables: age (years), height (cm), weight (kg), BMI-Body Mass Index (kg/m^2).

Categorical variables: age (18- <65 years and  $\geq$ 65 years), sex (male, female), child bearing potential (for females: yes, no), ethnicity (Hispanic or Latino, Not Hispanic or Latino), race (African American/African Heritage, American Indian or Alaskan Native, Asian – Central/South Asian Heritage, Asian – East Asian Heritage, Asian – Japanese Heritage, Asian – South East Asian Heritage, Native Hawaiian or Other Pacific Islander, White – Arabic/North African Heritage, White/Caucasian/European Heritage) and BMI (<18.5, 18.5 - <25, 25 - <30,  $\geq$ 30).

An additional summary will include age, sex and race for placebo group and combined GSK3196165 treatment groups.

##### Baseline efficacy parameters

Continuous baseline efficacy parameters and components will be summarised in a separate table.

##### Medical history

Prior and concomitant medical history will be summarised by reported term. Cardiac disorders will be shown separately.

#### Disease history

RA disease history will be summarised in form of disease duration (duration from formal RA diagnosis to first study medication administration) categorical ( $< 2$  years/  $\geq 2$  years) and as summary statistics (in months), RA functional class and time since start of RA symptoms (in months).

Separate by-subject listings of demographic data and other baseline characteristics, prior and concomitant medication, medical history, RA medication use and disease history will be provided.

## **4.7 Medication Use**

#### Prior and concomitant medication use

Prior and concomitant medications will be summarised by Anatomical Therapeutic Chemical (ATC) classification and randomised treatment group in separate tables. Medications that are both prior and concomitant will appear in both tables.

Medications that start and stop prior to the date of first dose of study medication will be classified as Prior only. If a medication starts before the date of first dose of study medication and stops on or after the date of first dose of study medication then the medication will be classified as both Prior and Concomitant. Medications will be classified as Concomitant only if they have a start date on or after the date of first dose of study medication.

If medication start and/or stop dates are missing or partial, imputations are done as described in section 4.5.1 and the dates will be compared as far as possible with the date of first dose of study medication. Medications will be assumed to be Concomitant only, unless there is clear evidence (through partial dates as described in section 4.5.1) to suggest that the medication started prior to the first dose of study medication. If there is clear evidence to suggest that the medication started prior to the first dose of study medication, the medication will be assumed to be both Prior and Concomitant, unless there is clear evidence to suggest that the medication stopped prior to the first dose of study medication. If there is clear evidence to suggest that the medication stopped prior to the first dose of study medication, the medication will be assumed to be Prior only.

Prior and concomitant corticosteroid use will be shown in a separate listing.

#### RA medication use

Prior and concomitant RA medication will be summarised by ATC classification and randomised treatment group.

#### Oral Corticosteroid use

Change from baseline in average daily prednisone dose will be summarised by visit. The number and percentage of subjects with  $\geq 25\%$  decrease from baseline and to below  $\leq 7.5$  mg/day will be summarised at Weeks 12, 24, 36, 48 and 52.

## 4.8 Treatment Compliance

Summaries will be based on the ITT population and will be provided by randomised treatment group and time period.

### Study Treatment

Treatment compliance for GSK3196165 will utilize the administered volume and compare it to the scheduled expected volume. The general formula for the compliance ratio (CR) is given as follows:

$$CR = \frac{\text{actual volume (mL)} * 100}{\text{expected volume (mL)}} \%$$

The expected volume is based on the planned number of doses (based on each subjects time in the study) and study treatment volumes provided in the protocol Section 6.1. If a subject completed the study without escalation, then the total number of doses would be 28 and the total expected volume for each treatment group would be as follows: placebo=16.8mL; 22.5mg=4.2mL; 45mg=8.4mL; 90mg=16.8mL; 135mg=25.2mL; 180mg=33.6mL. The actual volume is the sum of the volume of doses received in mL. If a subject escalates to 180mg dose, the 180mg volume times the number of doses would be included in the expected volume. The ratio will be summarised as a continuous variable as well as categorically (<80% and  $\geq 80\%$ ) and will be shown separately for administrations of randomised treatment and administrations after escalation.

Additionally, number and percentage of subjects who missed at least two doses of GSK3196165 will be summarised by period.

### Methotrexate

Numbers and percentages of subjects who increased or decreased their MTX dose or missed a MTX dose during the conduct of the study will be shown separately for administrations before escalation and after escalation.

A by-subject by-period listing of treatment compliance ratio for GSK3196165 will be provided.

## 4.9 Efficacy Evaluation

### 4.9.1 Statistical Considerations

#### 4.9.1.1 Hypotheses for Primary Endpoint and Dose-Response Relationship

##### Primary endpoint (remission at Week 24):

The study will test the null hypothesis that there is no difference between any dose of GSK3196165 and placebo in the proportion of subjects with remission (DAS28(CRP)<2.6) at Week 24 versus the alternative hypothesis that at least one of the GSK3196165 dose groups differs from placebo in the proportion of subjects with remission at Week 24.

H0: No difference between placebo and the 5 active doses

H1: At least one of the 5 active doses differs from placebo

#### Dose response relationship (change from baseline in DAS28(CRP) at Week 12):

The null hypothesis (H0) for the dose response relationship assumes that there is no effect of the test drug and hence no evidence of a dose response relationship with respect to the change from baseline in the DAS28(CRP) continuous score. This is equivalent to saying that none of the active doses differs from placebo:

H0: Placebo = 22.5 mg = 45 mg = 90 mg = 135 mg = 180 mg

Whereas the alternate hypothesis (H1) assumes that there is a significant relationship between GSK3196165 dose and response with respect to the change from baseline in the DAS28(CRP) continuous score. It is expected that this relationship will follow an Emax model or more generally is a monotone relationship:

H1: Placebo  $\geq$ 22.5 mg  $\geq$ 45 mg  $\geq$ 90 mg  $\geq$ 135 mg  $\geq$ 180 mg

#### **4.9.1.2 Multi-center Studies**

This study will randomise 210 subjects into 6 treatment arms, so that on average only 35 subjects per arm will be enrolled (although some arms may have larger patient numbers if inferior arms are dropped at the interim analyses). The number of sites (centres) may be roughly around 70, so that an adjustment of the analyses by centre will not be feasible.

For all analyses all sites, countries and regions will be pooled.

#### **4.9.1.3 Adjustments for Covariates**

Adjustment for the following covariates will be considered: baseline value, disease duration (<2 years,  $\geq$ =2 years), weight, age, and sex.

#### **4.9.1.4 Multiple Comparisons/Multiplicity**

For this phase II study no adjustment for multiple testing is planned.

#### **4.9.1.5 Interim and Final Analyses**

Two interim analyses, one primary endpoint analysis and a final analysis are planned during the course of this study. Unblinded results will be presented to the DRC where the decision to drop treatment arms or stop the study based on benefit/risk relationship or based on safety findings alone will be made as detailed in the DRC Charter or DRC Statistical Guidance document. See section [4.10.11](#) for additional DRC information.

The timing and content of each deliverable is summarised in the following table.

**Table 4 Interim and Final Deliveries**

Analysis	Timing	Deliverable	Unblinded Team	Main Objective
Interim 1	90 subjects complete Week 4	PAREXEL: ADAM datasets and demography table (see Table 5 )  GSK: efficacy displays (see Table 5 ) and PK if required	Unblinded PAREXEL programmers, GSK lead and QC statistician, DRC	Evaluate whether to stop the study based on: • Dose response relationship at Week 4 (i.e., if all doses have $> -0.4$ point difference over placebo using the Week 4 dose response model estimates for change from baseline in DAS28(CRP)).
Interim 2	90 subjects complete Week 12	PAREXEL: ADAM datasets and demography table (see Table 5 )  GSK: efficacy displays (see Table 5 ) and PK if required	Unblinded PAREXEL programmers, GSK lead and QC statistician, DRC	Evaluate whether to stop the study based on: • Dose response relationship at Week 12 (i.e., if all doses have $> -1.0$ point difference over placebo using the Week 12 dose response model estimates for the change from baseline in DAS28(CRP)). • Dose response relationship and predictive probabilities (i.e., if at least one dose $\leq -1.0$ over placebo using the Week 12 dose response model estimates but the predictive probabilities of seeing a 25% difference at Week 24 in DAS28(CRP) remission is $<30\%$ ). Evaluate whether to drop a treatment arm based on: • An individual dose with $> -1.0$ point difference over placebo using the Week 12 dose response model estimates for change from

				baseline in DAS28(CRP).
Week 24	All subjects complete Week 24 visit	PAREXEL: Unblinded Week 24 displays.	PAREXEL lead and QC biostatisticians and programmers, GSK.	Unblinded primary/secondary analyses, safety and PK.
Final	All subjects complete the study (follow-up visit at Week 62)	PAREXEL: All unblinded displays, including exploratory endpoints, SDTM and ADAM datasets.	PAREXEL lead and QC biostatisticians and programmers, GSK.	Final reporting for Study 201755.

Unblinded interim analyses will be conducted when 90 subjects (i.e. on average 15 per arm) have completed 4 and 12 weeks of treatment. Efficacy analysis for the interim analyses will not be analysed by PAREXEL but by GSK. These interim analyses will be aligned with the unblinded safety review of the DRC where possible, see section [4.10.11](#).

#### 4.9.1.6 Examination of Subgroups

A subgroup analysis for subjects with early RA (i.e. < 2 years disease duration before first study medication administration) will be conducted if there are at least 10% subjects with early RA in the ITT population.

Additionally, subgroup analyses for selected endpoints may be conducted by gender if an adequate number of subjects are represented in each subgroup.

The following endpoints will be summarised for all subgroups in the same way as done for the entire population:

- DAS28(CRP) remission at all assessment points
- Change from Baseline in DAS28(CRP) at all assessment points
- ACR 20/50/70 response rates at all assessment time points

The following outputs for key safety endpoints will be provided by randomised treatment group for all subgroups:

- Overall summary of AEs
- Number and percentage of subjects reporting an AE by SOC and PT
- Number and percentage of subjects reporting a serious AE by SOC and PT
- Summary of AESIs
- Summary of subjects with pulmonary findings

## 4.9.2 Key Efficacy Analyses

### 4.9.2.1 Interim Analyses

The outputs listed in [Table 5](#) will be produced at the efficacy interims. All data will be summarised using the Intent-to-Treat population.

The second interim analysis may allow an assessment of subjects with early RA (<2 years disease duration). Results may impact the proportion of subjects randomised to this subgroup.

**Table 5 List of Outputs for Interim Analyses (IA)**

Endpoint	Output	IA1	IA2	Produced by
n/a	Summary of Demography Characteristics – Disease History	Y	Y	PAREXEL 
DAS28(CRP) change from baseline	Summary of the Change from Baseline in DAS28(CRP) at Each Visit	Y	Y	GSK
	Plot of Mean and 95% CI of Change from Baseline in DAS28(CRP) by Visit and Randomised Treatment Group (1 plot)	Y	Y	GSK
	Plot of Mean and 95% CI of Change from Baseline in DAS28(CRP) Across Doses at Weeks 4, 8 and 12 (3 plots)	Y	Y	GSK
	Mixed Model Repeated Measures Analysis (MMRM) of Change from Baseline in DAS28(CRP) Through Week 12	Y	Y	GSK
	Plot of Least Squares Means and 95% CI of Change from Baseline in DAS28(CRP) (from MMRM)	Y	Y	GSK
	Dose Response Modelling of Change from Baseline in DAS28(CRP) at Weeks 4, 8 and 12	Y	Y	GSK
	Plot of Dose Response Model at Weeks 4, 8 and 12	Y	Y	GSK
DAS28(CRP) remission	Posterior Probability of the Difference in the Change from Baseline over Placebo < -1.0 at Week 12 for Each Dose	Y	N	GSK
	Proportion of Subjects in DAS28(CRP) Remission at Week 24	N	Y	GSK
ACR response	Predictive Probability of the Difference Over Placebo in the Proportion of Subjects in DAS28(CRP) Remission at Week 24 being > 25%	N	Y	GSK
	Proportion of Subjects with an ACR20/50/70 Response at Each Visit	Y	Y	GSK

 Produced by the unblinded programming team.

### DAS28(CRP) change from baseline

DAS28(CRP) scores and changes from baseline will be summarised for each visit. The mean change from baseline in DAS28(CRP) score and 95% CI will be plotted by randomised treatment group.

For change from baseline in DAS28(CRP) score, a mixed model repeated measures (MMRM) analysis will be conducted including all weeks up through Week 12. For the first interim the analysis will subset on those subjects with Week 12 DAS28(CRP) scores. The model will be fitted with fixed effects for randomised treatment group, visit, treatment by visit interaction and baseline DAS28(CRP), and visit within subject as a repeated effect. The covariance will initially be specified as unstructured covariance matrix. If SAS® gives a non-convergence warning, the

results will not be used – instead the warning will be stored and the spatial power law structure will be used in order to reduce the number of parameters to be estimated.

The point estimates and corresponding 95% CI for the treatment differences will be constructed using the residual error from the model; these estimates will be summarised and plotted for each randomised treatment group comparison over time.

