### **Dose-Response at Weeks 4, 8 and 12**

A plot of the mean change from baseline in DAS28(CRP) score and 95% CI versus dose will be provided separately for each of Weeks 4, 8 and 12.

The dose-response relationship for the change from baseline in DAS28(CRP) score will be evaluated at Week 4, 8 and 12 using a three parameter  $E_{max}$  model of the form:

$$Y = E_0 + E_{max} * [Di / \{ ED_{50} + Di \}]$$

where  $E_0$  is the placebo effect,  $E_{max}$  is the maximum achievable effect above placebo,  $ED_{50}$  is the dose at half  $E_{max}$  and  $Di$  are doses =0, 22.5, 45, 90, 135 and 180 mg.  $Y$  is a measure of change from baseline in DAS28(CRP) continuous score.

If this Emax model is not applicable then additional models will be investigated, including a four parameter  $E_{max}$  model with a slope factor  $B > 0$ :

$$Y = E_0 + E_{max} * [Di^B / \{ ED_{50}^B + Di^B \}]$$

and the model with the expected response as a linear function of dose:

$$Y = E_0 + E_1 * Di$$

Each of the models will be fitted to the data and their fit compared using the Akaike information criteria (AIC), where the model with the lowest AIC will be the primary model for inference. The additional models will be considered secondary models, and will not be utilised unless issues arise with the residual checks on the primary model. Distributional assumptions will be assessed by examining plots of the residuals from the primary model.

The final model parameters for the dose-response will be summarised; a plot of the dose-response relationship will be provided. The chosen models might differ between Week 4, 8 and 12. SAS outputs of all secondary models will be shown.

## Posterior Probabilities at Week 12

In addition to assessing the dose response model for the DAS28(CRP) change from baseline data at Weeks 4, 8 and 12, the posterior distribution for the Week 12 change from baseline in DAS28(CRP) will be calculated.

This will be derived assuming the data follow a normal distribution with mean  $\mu_i$  and precision  $\tau_i$  (where  $i=0$  is the placebo group and  $i=1-5$  are the treatment groups) and non-informative prior distributions for  $\mu$  and  $\tau$ :

$$\mu_i \sim N(0, 10^{-2})$$

$$\tau_i \sim Ga(0.001, 0.001)$$

Given the small number of subjects expected with Week 12 data at the first interim analyses, alternative prior distributions for  $\tau$  may be investigated.

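### The Interim 1 MMRM is limited to subjects who already have a Week 12 score, which gives up precision in one supportive display for no stated reason

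*SAP*

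**What the plan says.** SAP Table 4 sets the timing of Interim 1 as "90 subjects complete Week 4", and the text after the table repeats this for both interims: "Unblinded interim analyses will be conducted when 90 subjects (i.e. on average 15 per arm) have completed 4 and 12 weeks of treatment".

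SAP 4.9.2.1 opens with the population: "All data will be summarised using the Intent-to-Treat population". Table 5 then lists, for Interim 1 as well as Interim 2, a "Mixed Model Repeated Measures Analysis (MMRM) of Change from Baseline in DAS28(CRP) Through Week 12" together with a plot of its least squares means.

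The paragraph that specifies this model includes all weeks through Week 12 and then restricts it: "For the first interim the analysis will subset on those subjects with Week 12 DAS28(CRP) scores". No reason is given. On the variance structure it says: "The covariance will initially be specified as unstructured covariance matrix", with a spatial power structure as the replacement if the software warns of non-convergence.

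Later in 4.9.2.1, where the Week 12 posterior probabilities are described, the SAP allows other priors with this reasoning: "Given the small number of subjects expected with Week 12 data at the first interim analyses".

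The stop criterion that Table 4 lists for Interim 1 is a "point difference over placebo using the Week 4 dose response model estimates". The dose-response text in 4.9.2.1 carries no restriction to subjects with Week 12 data.

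**The concern.** An MMRM is normally chosen because it uses every observed visit from subjects whose follow-up is incomplete. At Interim 1 most incomplete follow-up will exist simply because the subject entered recently. Requiring a Week 12 score removes the Week 4 and Week 8 values of all those subjects and reduces the model to a complete-case analysis at Week 12.

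Two consequences follow. The data review committee would see MMRM estimates that are less precise than the data allow. It would also see two model-based Week 4 results for the same endpoint, one from the MMRM and one from the dose-response model, resting on different sets of subjects. The subset is in addition defined by something observed after randomisation, so it is not the ITT set named at the start of the section.

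**Working it through.** **Inputs from the documents.** Six arms; Interim 1 at 90 subjects through Week 4, on average 15 per arm (6 × 15 = 90, which reproduces the SAP's figure); between-subject SD of 1.0 for the Week 12 change (SAP 4.13.2), assumed here to apply at Week 4 too; dropout to Week 12 expected below 10% (Protocol 9.4.2).

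**Inputs assumed.** The accrual rate r, taken as 4, 6 or 8 per week; steady accrual; no dropout; within-subject correlation ρ between Week 4 and Week 12 of 0.5 to 0.8.

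**Subjects kept.** Week 12 falls 8 weeks after Week 4, so at the moment the 90th subject reaches Week 4, those who have reached Week 12 number n₁₂ = 90 − 8r.

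**Week 4 precision.** The standard error of an active-placebo difference is SD × √(2 / n per arm). With all 90 it is √(2/15) = 0.365. The inflation factor is √(90 / n₁₂).

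| r per week | n₁₂ | per arm | SE, subset | factor vs 0.365 |
|---|---|---|---|---|
| 4 | 58 | 9.7 | 0.455 | 1.25 |
| 6 | 42 | 7.0 | 0.535 | 1.46 |
| 8 | 26 | 4.3 | 0.679 | 1.86 |

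More than half of the 90 are lost only if 90 − 8r < 45, that is r > 5.6 per week, or about 0.08 per site per week over roughly 70 sites (SAP 4.9.1.2). Dropout of 10% would lower the counts to about 52, 38 and 23. Accrual that ramps up makes the loss larger: if the rate rises linearly from zero and the 90th subject enters at week 24, the number kept is 90 × (16/24)² = 40, against 90 × 16/24 = 60 under steady entry.

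**Week 12 precision.** Deleting the restriction adds no Week 12 observations; the gain comes only through correlation with earlier visits. Treating Week 4 and Week 12 as the two visits, the variance using all data is (2·SD²/n₁₂ per arm) × [1 − ρ²(1 − n₁₂/90)]. With n₁₂ = 26, 1 − 26/90 = 0.711, and the subset SE is 0.679.

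| ρ | bracket | SE, all data | subset ÷ all data |
|---|---|---|---|
| 0.5 | 0.822 | 0.616 | 1.10 |
| 0.7 | 0.652 | 0.548 | 1.24 |
| 0.8 | 0.545 | 0.501 | 1.35 |

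**Selection.** A two-visit simulation with ρ = 0.7, true contrasts near −0.80 at Week 4 and −1.30 at Week 12, and dropout related to Week 4 response gave the following. With 10% dropout in both arms, the subset contrasts showed no visible bias. With 2% on active and 18% on placebo, the subset contrasts moved to about −0.68 and −1.22, while the fit to all data stayed at about −0.80 and −1.30.

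**The case against.** The case for leaving the plan alone is substantial, and most of it stands.

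- *The loss is one output and its plot.* Table 5 also gives the committee, at Interim 1, summaries and mean plots of DAS28(CRP) change by visit, dose-response models at Weeks 4, 8 and 12, and ACR response by visit, none of them stated to be restricted. The Week 4 data do reach the committee.
- *A reader might infer that most of the 90 subjects are discarded.* The documents do not support that as a count. No accrual rate is given, and below about 5.6 per week a majority is kept. The SAP's remark about a small number with Week 12 data points towards heavy loss but puts no figure on it.
- *A reader might infer a biased completers analysis.* Most exclusions are administrative: the subject has not yet reached Week 12. That costs precision without selecting on outcome. Rescue contributes nothing, because data are set to missing for rescue only from Week 14 (SAP 4.5.2.1). Nor is a Week 12 score identical to finishing 12 weeks, since SAP 4.5.3 can assign a late early-withdrawal visit to Week 12.
- *A reader might infer that the stop decision is weakened.* The listed criterion uses the Week 4 dose-response model, which has no such restriction. Other Interim 1 criteria are left to the DRC Statistical Guidance Document, which is not among the documents reviewed, so any use of the MMRM there cannot be judged.
- *A reader might object that an unstructured matrix cannot be fitted to so few subjects.* The SAP already provides the spatial power fallback for non-convergence.

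None of this supplies a reason for the restriction.

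**Conclusion.** The point holds as a modest, avoidable loss of precision in the Interim 1 MMRM and its least squares means plot. Under steady accrual of 4 to 8 per week, no dropout and a common SD, Week 4 standard errors are 1.25 to 1.86 times what the available data allow. The Week 12 penalty is smaller, about 1.10 to 1.35 with 26 Week 12 subjects and correlations of 0.5 to 0.8. Both ranges rest on an accrual rate that neither document states, and the second also on assumed correlations.

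Selection bias is a secondary and conditional matter: it needs dropout or other missingness before Week 12 that differs between arms and is related to response. The conclusion should not be extended to the listed Interim 1 stop criterion, to the interim as a whole, or to the Week 24 primary analysis. It is a free improvement, not a flaw that threatens the trial.

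**What to change.** In SAP 4.9.2.1, delete the sentence that restricts the Interim 1 MMRM. State instead that at each interim the model is fitted to all ITT subjects with at least one post-baseline DAS28(CRP) value through Week 12 at the data cut, under the set-to-missing rules already in the plan. Keep the existing covariance specification and its fallback. Show the number of subjects contributing at each visit and arm, so that the committee can see how few support the Week 12 estimates.

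If a display confined to subjects with Week 12 scores is wanted, keep it as a supplementary output and label it so.

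The cost is one sentence of SAP text. No extra data, subjects, visits or design change are needed.
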